5.1.2 Patient-level analysis – mixed effects models

First, linear mixed effects models with random intercepts and slopes for school, and fixed effects for the school-level intervention, time, and time-by-intervention interaction (the estimate of interest) will be applied. Likewise, the main effect for the child-level intervention and a time*intervention interaction term will be included in the model, and variation across multiple measurements on a child within a school will be accounted for by child-level random effects. This approach then becomes a three-level model with explicitly modeled random effects at the school and child levels.

Synergy of the effect of the two interventions will be estimated by the 3-way interaction between time, the school-level intervention, and the child-level intervention along with all corresponding two-way interactions.

Models will use numerical quadrature with least 12 quadrature points. Models with 16 quadrature points will be used to check sensitivity of results to numerical integration.

This and other individual-patient-level methods can be more efficient (smaller confidence bounds) than cluster (school)-level models. (Hayes and Moulton, section 11.4.2)

We shall exploit mixed effects models to estimate the degree of variation of effects across the 36 schools, both the 18 intervention schools and the 18 control schools by estimating the random slope component of variance and asking whether the observed variation across schools is greater than that expected at random.

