The overall design will stratify participating schools into at least 5 groups to enhance balance at baseline in school characteristics (size, location, charter status). Randomization of schools to the school-level intervention (S⁺) or usual practice (S⁻) will be stratified by these predefined groups. At the time asthma patients present in the clinics and consent to participating, these patients will be randomized to navigator assistance (child-level intervention) (A⁺) or usual care (A-), and that randomization will be stratified by school and clinic of recruitment. Allocation concealment will be preserved by randomly permuted block, and this approach will also preserve balance of intervention arms within schools over time. This randomization plan will produce a 2by-2 factorial design, partly clustered (by school). (Table 1) Schools and children are followed over time.

Table1	Child-level		level
		intervention	
		A+	A-
School	S+	a	b
Level	S-	c	d
	none	e	f

The proposed design results in 6 groups of children. The cells a,b,c,d will permit comparison of any of the 3 combinations of school and child intervention (a,b,c) against the group that has neither(d). At the same time, it will permit marginal analysis of the effect of the school intervention (a+b vs c+d), and the marginal effect of the navigator intervention (a+c+e vs b+d+f). For each of the cells of interest, we collect baseline data on

children and then follow schools and children over time. This design avoids contamination and interference through cluster randomization but benefits from added power of a longitudinal analysis. The factorial layout permits estimation (and testing) of interaction between the school and

individual interventions. It also allows for use of data from children who are from nonparticipating schools.

3 Randomization

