3.1 Randomization of Schools

Schools were randomized in several waves to meet the evolving requirements of the study design.

Randomization Wave 1

For the cluster randomization of the 22 schools, we adopted the following approach. First, because two of the 22 schools were charter schools, we immediately paired them and randomly assigned one of the pair to the intervention and the other to control.

Second, for the remaining 20 schools we implemented covariate constrained randomization to achieve balance on the three key covariates: enrollment size, facility index (%), and percent with attendance>- 95% of the time. These 3 covariates are all continuous. For that reason, conventional stratification becomes problematic because it requires categorizing these continuous factors.

There is a fundamental contradiction between the realities of cluster randomized designs (few sites/clusters from which to sample) and the needs for balance in the resulting design (site pairings that lead to comparable groups of sites). For that reason, we used simulation methods as well described in the literature (Carter 2008; Nietert 2009; Ivers 2012; Moulton 2004;) also as "restricted randomization" or "covariate balanced randomization". This approach seeks to achieve balance for each of the specified characteristics of the clusters (schools).

In each simulation we assigned the 20 schools at random into 2 groups. Then we tested the resulting groups for differences in group means of enrollment, facility score, and attendance. These were the pre-specified school characteristics needed to balance. We then compared these intergroup differences in means to pre-set constraints. In our case we chose a mean difference constraint between schools groups of 10 students for enrollment, 3 for facility percent, and 3 for attendance percent. These constraints we regarded as narrow given the range of the distributions (See Table AX). With these constraints on means alone, however, we found in testing that the distributions could differ in range (and variance). For that reason, for both enrollment and for attendance, we added two more limits on the differences in ranges by school group: 50 for enrollment and 5 for attendance. Altogether, there were 5 constraints.

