In testing we found that the yield of balanced treatment allocations across schools was 3 in 1000. For that reason, we proceeded with 2000 simulations to be able to achieve at least one balance allocation of schools. From the resulting set of balanced allocations, we randomly selected one allocation of 20 schools into two groups.

We accomplished this simulation-based randomization with a custom-written program in Stata v 15.1 after finding that published alternatives were too slow and insufficiently flexible for our dual task of achieving balanced means and ranges. The final version of randomization proceeded with a program seed to ensure reproducibility.

	or service services	1 20 5011001	•	
School	Mean	Median	Min	Max
Feature				
Enrollment	463	487	242	644
Attendance (% of students 95%+)	33	30	20	79
Facility Condition Index %	38	39	<1	79

 Table AX1. School Characteristics for balancing. N=20 schools

Wave #2 Second Wave of Public Schools (November 2018)

The second wave of public schools used the same approach as Wave #1. There were 8 public schools in this wave. Using the same program and criteria as in the first wave, we used the same program (modified for only 8 schools) to arrive at 4 schools assigned to intervention and 4 assigned to controls.

Wave #3 Charter School Randomization (February 2019)

Owing to the small number of schools, the lack of data on facility condition, and the need to balance on several factors, we paired the 6 candidate schools and then when the pairs were formed, we randomized one school in each pair to intervention and the other to control.

The primary criterion for pairing was % of days with 95% or greater attendance. That criterion led to the pairing of two of the 6 schools (high attendance). Of the four remaining schools, they were pair on the basis of facility condition and enrollment. Randomization assignment then was by pair. We generated 6 random numbers via a single program from a random uniform generator (using Stata v 15.1) and assigned in order two number to each of the 3 pairs. Once assigned number, each pair then had a school with a higher random number a school with a lower random number. The school with the higher random number became the intervention school in the pair. All decisions about pairing criteria and actual pairing based on those criteria were agreed upon at a meeting on 02/21/2019. Random numbers were generated on 02/22/2019.

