Oral Steroid courses in the last year	None 1 course 2 courses 3 5 courses
ED With include - But describe in categories	>5 courses
ED VISITS in the last year	0, 1, 2, 3+
Continuous – Describe in categories Inpatient visits in the last year Continuous—Describe in categories	0,1,2, 3+

Data on height and weight, and BMI, and BMIz, will be downloaded from EPIC. BMI categories of interest are <85th percentile, 85th to 95th percentile, and 95% percentile or greater. Height is not done at each encounter. For that reason, height must be carried forward from the last available measurement time. This practice, though common, can result in a bias toward higher than actual BMI over time. Adjustments (e.g., interpolation) of height for measurement times between height measures is possible. If any interpolation of height, we shall do so without regard to measures of outcome.

For that reason, we shall first examine balance across the 4 treatment groups in child-level characteristics. To that end, we shall use conventional balancing diagnostics, such as comparison of percentages of patients by categorical factors and by standardized differences for continuous

factors, and/or comparisons of distributions. All will be supplemented by graphical display. These diagnostics are programmed and explained in the R program "cobalt" (Greifer 2019).

Treatment assignment model

Covariates that do not demonstrate balance will be included in an initial multinomial logit model (with the 4 treatments as outcomes). Then using generalized propensity scores, we will develop inverse probability of treatment assignment weights. This approach will then result in estimates of average treatment effects in the response model.

Response model—to estimate expected values over time

The response model will be a weighted longitudinal model using splines for time and time by treatment interaction terms. This model will result in the estimation of expected values at any given time post randomization for any of the four treatment categories.

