5.1.3 Patient-level analysis – marginal models

Second, marginal models using generalized estimating equations (Fitzmaurice 2011) will produce robust estimates that adjust for clustering at the school level. These methods tend to be robust for

non-continuous outcomes (non-identify link models) and those outcomes will likely apply to our outcomes of asthma control (possibly a log gamma model) and number of symptom days (possibly a log link Poisson or negative binomial model). In contrast to mixed effects models, marginal models do not rely on numerical integration. In addition to generalized estimating equations, quasi-least squares regression (Shults and Hilbe, 2014) will also be implemented. Quasi-least squares regression is an approach for estimation of the correlation parameters that is in the framework of generalized estimating equations; it allows for application of correlation structures that were previously unavailable for generalized estimating equations and can sometimes be implemented when generalized estimating equations fails to converge.

Marginal models tend to work poorly for designs with small numbers of clusters. In our case, the number of clusters (36) is relatively large. Nevertheless, we shall implement at least one method for adjusting for a number of clusters that is not large, as implemented in Stata's program xtgeebcv program (Gallis 2019) and R's program "saws" (Fay and Graubard 2001).

5.1.4 School-level analysis -- randomization-test-based methods.

Third, assumption-free, randomization-test-based (permutation test) methods that do not rely on assumptions of parametric models will also be applied. (Berger, 2000; Good, 2005; Small, 2008; Tang 2009; Rosenbaum 2002). (Also see Hayes and Moulton 2017)

We will use conventional levels of statistical significance (p=0.05) for all pre-specified comparisons for these aims. We shall not apply Bonferroni corrections for estimates from different modeling methods that use the same specification.

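### The school-effect models leave out the factors that constrained school allocation, and the permutation test names no reference set: a conditional loss of precision, not a bias

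*SAP*

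**What the plan says.** **Allocation.** SAP section 2 is written as a plan: "The overall design will stratify participating schools into at least 5 groups". SAP 3.1 reports what was done. For the 20 wave-1 public schools, "we implemented covariate constrained randomization to achieve balance on the three key covariates": enrollment, facility index and attendance, with three limits on mean differences and two on differences in range. The eight wave-2 public schools were allocated "Using the same program and criteria as in the first wave". Two charter schools formed a pair in wave 1, and six formed three pairs in wave 3. The wave-3 text cites "the lack of data on facility condition", then says of four of those schools that "they were pair on the basis of facility condition and enrollment".

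**Models.** In SAP 5.1.2 (mixed effects models) the S part has "fixed effects for the school-level intervention, time, and time-by-intervention interaction (the estimate of interest) will be applied". Child-intervention terms and school and child random effects are added. Protocol 6.4 gives the same model. The GEE and quasi-least-squares models in SAP 5.1.3 name no school factor.

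**Other adjustment rules.** The balance check and weighting concern children: "we shall first examine balance across the 4 treatment groups in child-level characteristics". SAP 5.3 adds covariates tied to dropout. SAP 5.2 uses the school randomization factors only to pool sparse schools. SAP 6.1.1 treats school factors, including charter status, as possible effect modifiers.

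**Permutation test.** SAP 5.1.4 says only that "assumption-free, randomization-test-based (permutation test) methods that do not rely on assumptions of parametric models will also be applied".

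**The concern.** When allocation is forced to balance a factor, the S contrast no longer varies with that factor from one possible allocation to the next. A model that omits the factor still counts its contribution to between-school spread as noise. If the factor predicts change in both arms, the reported standard error is too large, the interval too wide and the test conservative. The weighting rule would not repair this. It covers child characteristics only and acts only on observed imbalance, which the design was built to prevent.

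The permutation test has the matching problem. It is exact when its reference set is the set of allocations that could have occurred. Shuffling all 36 labels freely includes allocations that the scheme ruled out. Because the set is not stated, two analysts following this SAP could reach different p-values, whatever the factors predict. That matters because the SAP intends to read agreement among its three approaches as evidence of robustness.

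At stake are the precision of the S contrasts and the reproducibility of one of three pre-specified analyses. Child-level contrasts (A in the SAP, P in the protocol) are within-school comparisons and little affected.

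**Working it through.** **Inputs (SAP section 8).** 36 schools, 18 per arm, 12 children each; child-level variance 1.0; between-school variance 0.0625; S effect 0.5 SD. Alpha is 0.05 (SAP 5.1.4), taken as two-sided. R², the share of between-school variance in change that the factors explain, is not in the documents. I assume 0, 25, 50 and 75%.

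**1. Reproduce the plan's figure.** Variance of a school mean = 0.0625 + 1/12 = 0.1458. SE(S) = √(2 × 0.1458/18) = 0.1273. Power = Φ(0.5/0.1273 − 1.96) = 0.975, against 0.97 stated for n = 432.

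**2. Ideal gain, factors acting in both arms and fully balanced.** The true variance of a school mean is 0.0625(1 − R²) + 1/12, while the unadjusted model still reports about 0.1458.

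| R² | True SE | True SE / 0.1273 | Real alpha of unadjusted test | Power, unadjusted to adjusted |
|---|---|---|---|---|
| 25% | 0.1203 | 0.945 | 0.038 | 0.981 to 0.986 |
| 50% | 0.1128 | 0.886 | 0.027 | 0.987 to 0.993 |
| 75% | 0.1049 | 0.824 | 0.017 | 0.992 to 0.998 |

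The effect is bounded because the school component is only 0.0625/0.1458 = 43% of the variance of a school mean.

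**3. Simulation with degrees of freedom and imperfect balance counted.** School covariates were invented to fit SAP Table AX1. Wave-1 allocations were drawn from the 184,756 possible splits that met the five limits. The adjusted model used six school-level terms.
- Both arms: adjusted intervals 4–5%, 10–11% and 17–18% narrower at 25, 50 and 75%. Unadjusted type I error 0.038, 0.027–0.030 and 0.019–0.023; adjusted 0.048–0.052. Power at 0.5 SD rises from 0.973 to 0.978 at 25% and from 0.978–0.979 to 0.988–0.989 at 50%. Contrasts between single cells gain 0.7–1.0 and 2.4 points.
- Intervention schools only: intervals change by 0, −1 to −1.5 and −2 to −3%, and power by no more than 0.4 points.
- Factors predict nothing: six terms widen intervals by 1.7% with equal schools, 2.9% if the coefficient of variation (CV) of school size is 0.6, and 4.8% at 1.0. Four terms cost about 1–3% over the same range.

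**4. Form of the time terms.** In a spline-time mixed model at 50% (both arms), the SE of the 12-month S contrast was 0.126 unadjusted, 0.124 with factor main effects only, and 0.111 with factor-by-time terms. Linear and spline factor-by-time terms agreed to three decimals. The interaction is therefore needed and the spline form is not.

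**5. Permutation test, type I error (both arms; 25, 50, 75%).** Unrestricted 18/18 shuffling: 0.037–0.043, 0.027–0.028, 0.019–0.025. Actual scheme: 0.050–0.056, 0.046–0.051, 0.048–0.052. At the stated yield of 3 in 1000, wave 1 has about 184,756 × 0.003 = 554 admissible splits. The four charter pairs give 2⁴ = 16 arrangements. With at least 2 wave-2 splits, the set has at least 554 × 16 × 2 ≈ 17,700 members, so p-values are not coarse.

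**6. Wave 2 cannot be rebuilt from the text.** Eight schools have 70 possible 4/4 splits. At the wave-1 yield, 70 × 0.003 = 0.21 would qualify. The limits actually applied must come from the program.

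**The case against.** The best case against acting is that little is at stake. There is no bias, the test errs on the safe side, and planned power for the main S contrast is already 0.97. Cell-contrast gains at 25–50% are smaller than the gap in the SAP's own table between 0.88 and 0.83, two contrasts with the same true effect. All of this stands, and it keeps the point minor.

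The both-arms scenario is also the less documented one. SAP section 8 derives 0.0625 from variation in effect size across schools, and Table 6.1a hypothesises less improvement under the school intervention in certain schools. Both fit the intervention-schools-only reading, where adjustment gains almost nothing. A reader might take Table 6.1a as showing that the factors predict change in every school. It does not.

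Adjustment has costs when schools are unequal, and SAP 6.1.1 notes small numbers of children in some. At 25% explained, the six-term gain falls from 4.4% to 3.5% (CV 0.6) or 1.4% (CV 1.0). In an approximation to the GEE with one small-sample correction, adjusted type I error was 0.054–0.055 at CV 0.6. At CV 1.0 it was 0.060–0.069, against 0.042–0.058 unadjusted. This argues for few terms and for keeping GEE adjustment as a sensitivity analysis.

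Finally, section 2 states an intention and 3.1 reports the conduct, and missing facility data may mean incomplete data. These are wording to reconcile. They are not evidence that allocation went wrong. Nor does the wave-2 arithmetic show that the limits were unmet: it assumes those schools resemble wave 1, and the program was modified for eight schools.

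**Conclusion.** The point holds as a conditional gain in precision and a gap in specification. The S models omit the factors used to allocate schools, and the permutation reference set is unstated. A reader might infer that the S analysis is invalid, that false positives are inflated or that the power table is overstated. None of these follows: the unadjusted test is nominal if the factors predict nothing and conservative if they predict change.

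If the factors act in both arms, adjusted S intervals are about 4% narrower at 25% and 10% narrower at 50% of school variance explained, with about 1 point of power at most for the main S contrast at 0.5 SD. If they act only in intervention schools, the gain is close to nil. The shares are assumed, the simulated school covariates are invented, and neither the log-gamma GEE nor the child-level weights were simulated. The need to name the permutation set depends on none of this. It is a change to consider, with medium confidence.

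**What to change.** 1. **Mixed model for S.** Pre-specify four school-level terms: enrollment, facility index, attendance and charter status. Give each a linear time interaction, include them regardless of observed balance, and report the unadjusted model alongside.
2. **GEE.** Adjust only with the small-sample correction already planned in SAP 5.1.3, as a sensitivity analysis.
3. **Permutation test.** State that it runs over the re-allocations the actual scheme allowed: wave-1 splits meeting the five limits, wave-2 splits meeting the limits actually applied (recovered from the randomization program), and swaps within charter pairs. Permute schools as originally allocated, and say how this fits the pooling rule in SAP 5.2. That rule merges schools within the realised arm, so a merged unit cannot always be re-allocated.
4. **Wording.** Say that SAP 3.1, not section 2, describes the school allocation, and reconcile the two wave-3 statements on facility data. If the index is missing for charter schools, set it to a constant alongside the charter term.
5. **Status.** The SAP was finalized on 13 September 2022, so record this as a dated amendment, labelled post hoc if outcomes have been examined.

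**Cost.** Four school-level degrees of freedom (34 to 30). If the factors predict nothing, S intervals are about 1–3% wider, depending on how unequal the schools are. The wave-2 limits must be retrieved; no new data collection is needed.
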